12.3 Laboratory

12.3.1 Parameters

Laboratory Tests	Parameters		
Hematology	Haemoglobin Red blood cell count (RBC) Red cell distribution width (RCD) Haematocrit/Packed cell volume (PCV)	RBC Indices: Mean cell volume (MCV) Mean corpuscular haemoglobin (MCH) Mean platelet volume (MPV) Platelets	White blood cell (WBC) count with Differential: Neutrophils Lymphocytes Monocytes Eosinophils Basophils
Clinical Chemistry	Sodium Potassium Chloride Bicarbonate Anion Gap Urea Creatinine	Albumin Alkaline phosphatase (ALP) Gamma-glutamyl transferase (GGT) Alanine Aminotransferase (ALT)	Creatinine Kinase (CK)
	eGFR Uric acid Glucose (non-fasting) Calcium Ionised Calcium	Phosphate Total Protein Globulin Bilirubin	Aspartate Aminotransferase (AST) Lactate dehydrogenase (LD)
Routine Urinalysis (if positive urine dipstick)	Bilirubin, Specific gravity, pH, Nitrate, Protein, Leucocyte esterase, Blood, Ketones, Glucose, Urobilinogen, Creatinine.		Microscopic examination (if blood or protein is abnormal)

Pregnancy testing	Highly sensitive serum
FSH	FSH for confirmation of post memopausal status
Other Tests	Serology: (HIV antibody, hepatitis B surface antigen [HBsAg], and hepatitis C virus antibody)

12.3.2 Biostatistical methods

Individually for Part A and Part B, all laboratory parameters will be listed with flags for values outside the reference ranges and values considered to be clinically significant by the investigator.

Each parameter will be summarised descriptively (including actual values and changes from baseline) by visit and treatment.

Categorical interpretations of each record (Normal, Abnormal – Not Clinically Significant (NCS), Abnormal – Clinically Significant (CS)) will be summarised for each scheduled visit, as well as the worst case, in a separate set of tables, ordered as follows from best to worst case: Normal, Abnormal – NCS, Abnormal – CS. The worst case finding will reflect all post-baseline assessments, including unscheduled and early discontinuation visits.

Maximum shift tables will also be presented for hematology and chemistry variables, presenting a summary of the shifts from baseline values to the most extreme post-baseline value, where all scheduled and unscheduled visit results will be assessed to determine the maximum shift. The maximum shift will be determined based on the absolute change from baseline, considering both shifts in the negative and positive direction. Both the baseline and maximum shift values will then be converted to “Low”, “Normal” or “High” using the associated reference ranges.

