2. PROJECT OVERVIEW

2.1 Study Design

This is a Proof-of-Concept study that consists of two parts

2.1.1 *Part A (single ascending dose study)*

Part A will be a double-blind, randomized, placebo-controlled, single ascending dose (SAD) study within 8 healthy volunteers of intravenous administration of LAT8881 over 5 minutes.

The SAD study will enrol 8 participants and each participant will have three treatment days, 1 infusion per dosing day on days 1, 4 and 7 as well as two short visits for safety blood sampling on

[figure not shown]
Day 3 and 6 (Figure 1). The 8 participants will be split into two groups of 4 participants each (3 IMP and 1 placebo), with the two groups dosed a few days apart.

Participants will arrive on the morning of each treatment day, receive a single infusion, leave that afternoon (no overnight stay). Participants on a given dosing day will be dosed at staggered intervals as determined by PI.

Treatments will be on Days 1 (0.8 mg/kg), Day 4 (1.2 mg/kg) and Day 7 (1.8 mg/kg) or placebo to allow sufficient washout and consideration of any safety observed following each dosing day. Day 3 and 6 safety blood results will be reviewed prior dosing on the following dosing day.

Participants will fast for 8 hours pre-dose and 4 hours post dose for each dosing occasion. Participants will be randomised, so on each treatment day per group, 3 participants receive LAT8881 and 1 receive placebo (different participants to receive placebo each treatment day). Participants will remain at the clinic until 6 hours post-infusion in order to collect blood samples for PK analysis and for review of safety and tolerability. Safety assessments will be reviewed in a clinic exit visit 7 days after the last infusion.

Figure 1: Part A Study Design

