3.2 Statistical Programming

3.2.1 Baseline

Baseline will be defined as the last available assessment prior to the first IMP administration. For part B, baseline will be assigned separately for the two treatment periods..

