12.7.2 Biostatistical methods

ECG parameters will be listed for all participants and time points.

Observed values, and absolute change from baseline, will be summarised descriptively for all ECG parameters by scheduled visit and timepoint for part A and by sequence and overall for part B.

The number and percentage of participants with ECG findings will also be summarized by scheduled visit and timepoint part A and by sequence and overall for part B. This table will include a summary of the number and percentage of participants with abnormal results for each parameter at each timepoint, using the set of normal ranges provided.

A maximum shift table will also be presented for ECG Result, presenting a summary of the shifts from baseline values to the most extreme post-baseline value, where all scheduled and unscheduled visit results will be assessed to determine the maximum shift, ordered (best to worst case) by Normal, Abnormal – NCS, Abnormal – CS.

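### In Part A the laboratory worst-case table and the laboratory and ECG-result maximum-shift tables have no per-infusion window, so one participant's worst finding can count under up to three treatment columns; Part B needs only clarification, except that its ECG tables do not separate the treatments.

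*SAP*

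**What the plan says.** **The window.** For laboratory categories, SAP 12.3.2 states: "The worst case finding will reflect all post-baseline assessments, including unscheduled and early discontinuation visits". For the maximum shift, 12.3.2 (haematology and chemistry) and 12.7.2 (ECG result) use the same clause: "where all scheduled and unscheduled visit results will be assessed to determine the maximum shift". None of the three rules stops at the next dose.

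**Part A.** SAP 2.1.1 says that "each participant will have three treatment days", with different people on placebo each day. SAP 2.2 gives 6 active and 2 placebo per dosing day. SAP 3.2.5 sets columns for each dose, all doses, pooled placebo and total. The baseline in SAP 3.2.1 is single: "Baseline will be defined as the last available assessment prior to the first IMP administration". No rule in the SAP assigns a Part A record, or a worst value, to a treatment.

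**Part B.** SAP 3.2.1 adds: "For part B, baseline will be assigned separately for the two treatment periods". SAP 3.2.6 gives each record in visit-based tables the treatment of its period and shows Day 9/ETV in the total column only. Protocol 21.1 and SAP 12.2 call for safety summaries by treatment within period. For ECG, however, SAP 12.7.2 says that values "will be summarised descriptively for all ECG parameters by scheduled visit and timepoint for part A and by sequence and overall for part B".

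**The concern.** A worst-case rule that runs from baseline to the end of follow-up suits a parallel-group trial, where everything after baseline belongs to one treatment. In Part A the same person contributes to several columns. If the person's overall worst value is carried into each of them, an abnormality that follows a LAT8881 infusion also appears under placebo, and one that follows the highest dose also appears under the lower doses. Placebo and dose columns then move together, and so do the dose columns.

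Incidence and severity of laboratory abnormalities is a Part A primary endpoint (SAP 2.4.1), and the worst-case table is its participant-level summary by category. The ECG shift table matters less, because the ECG primary endpoint is change in parameters, which is summarised by visit and timepoint.

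**Working it through.** The plan gives no abnormality rate, so there is no figure of its own to reproduce. The check counts column membership and then illustrates the effect with assumed rates.

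**Step 1: who sits in which Part A column (SAP 2.1.1, 2.2)**
- Placebo: 2 per day × 3 days = 6 different people, each with 1 placebo and 2 active infusions.
- Always active: 8 − 6 = 2 people, each with 3 active infusions.
- Active infusions: 6 × 3 = 18, of which 6 × 2 = 12 went to people who are also in the placebo column.
- Each dose column holds 6 people: 4 of the placebo rotators and the 2 always-active people.

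With one baseline before the first dose and all later results eligible, results after those 12 of 18 infusions can reach the placebo column. If instead each treatment's window opened at its own dose and ran to study end, only later infusions could leak: 2 × 2 from Day 1 placebo, 2 × 1 from Day 4 and none from Day 7, or 6 of 18. The single baseline in 3.2.1 points to the first reading.

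**Step 2: expected proportions**

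Assume independent chances of an abnormal finding per infusion: *a* after active (the same at every dose) and *p* after placebo.
- Window ending at the next dose: difference = a − p.
- All data, placebo column: M = 1 − (1 − a)²(1 − p).
- All data, always-active person: T = 1 − (1 − a)³.
- All data, dose column: (4M + 2T)/6.
- All-data difference: (T − M)/3 = (a − p)(1 − a)²/3.

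For a = 0.30 and p = 0.05:
- M = 1 − 0.49 × 0.95 = 0.5345
- T = 1 − 0.343 = 0.657
- Dose column = (4 × 0.5345 + 2 × 0.657)/6 = 0.5753
- Difference = 0.5753 − 0.5345 = 0.0408, against 0.25 with a window

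| Active | Placebo | Difference, windowed (points) | Difference, all data (points) | Share kept |
|---|---|---|---|---|
| 10% | 5% | 5 | 1.35 | 27% |
| 20% | 5% | 15 | 3.20 | 21% |
| 30% | 5% | 25 | 4.08 | 16% |
| 30% | 10% | 20 | 3.27 | 16% |
| 50% | 10% | 40 | 3.33 | 8% |

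The share kept is (1 − a)²/3, so under these assumptions it never exceeds one third. The reason is structural: the placebo rotators carry the same worst value into every column they belong to, so only the 2 always-active people can produce an expected difference.

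**Step 3: Part B, passages side by side**
- *Laboratory.* With a baseline per period and records assigned by period, a Day 1 result belongs to the Period 1 treatment and a Day 2 result to Period 2. The shrinkage does not follow. Two points stay open. The 3.2.6 rule is written for visit-based tables; SAP section 3 excludes unscheduled and early-withdrawal visits from such tables, while 12.3.2 includes both in the worst case. It is therefore unclear whether 3.2.6 reaches this table. Nor is a column named for unscheduled or ETV results.
- *ECG.* The stated columns are sequences. Each sequence contains both treatments, so the tables hold no LAT8881-placebo contrast, which conflicts with Protocol 21.1 and SAP 12.2.

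**The case against.** - **Part B is mostly handled.** A reader might infer that the Part B laboratory difference is halved or erased. That would require ignoring the period baseline, the record-by-period rule and the call for safety summaries by treatment within period. The documents do not support it.
- **Including unscheduled visits does not cancel treatment assignment.** A reader might take that inclusion as displacing the period rule. It is more naturally an exception to the general exclusion in SAP section 3: it settles which visits count, not which treatment they belong to. This stands.
- **ECG.** A reader might also infer a diluted Part B ECG contrast. With sequence columns there is none to dilute; the fault is a different one.
- **Columns may be set elsewhere.** The SAP text does not name the columns of the worst-case and shift tables, and the mock tables mentioned in SAP 3.2.4 are not available here. So the miscount is what a literal reading produces, not a calculation the plan spells out. This stands, but the derivation rule belongs in the SAP text.
- **Limited consequence.** The tables are descriptive and cover 8 and up to 20 participants. Flagged listings and by-visit tables remain, clinically significant abnormalities must be recorded as adverse events (Protocol 20.7.1), and no stated decision rule uses these tables. This confines the harm to the summary tables. It does not make a wrong incidence table right.

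**Conclusion.** The point holds for Part A. Read literally, SAP 12.3.2 and 12.7.2 let one participant's worst finding enter up to three columns, and nothing else in the SAP prevents it. Over the assumed rates tried, the dose-placebo contrast falls to between 8% and 27% of its windowed size. Those percentages rest on assumed, independent rates that are equal across doses, and on the reading that all data after a single baseline are used. The overlap in column membership does not depend on the rates.

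For Part B the laboratory issue is a clarification only. The ECG tables have a separate, definite fault: sequence columns cannot show a treatment difference. The change is worth making before the final tables are produced, but it does not affect the efficacy analysis or the listings.

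**What to change.** In SAP 12.3.2 and 12.7.2:

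1. Derive worst case and maximum shift per participant and infusion, using results from the start of that infusion to the start of the next.
2. Name the baseline used for Part A. For Part B, state that the period baseline and the record-by-period rule apply to these tables.
3. Assign unscheduled results by the same window.
4. Show Day 9/ETV (Part B) and the Day 14 ECG (Part A) in the total column only, as 3.2.6 already does for Day 9.
5. Tabulate by treatment, including the Part B ECG tables.

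The protocol schedules already provide usable samples: Part A laboratory tests at 6 hours and on Days 3 and 6, and Part B pre-dose samples. The cost is a few sentences and a by-infusion derivation in the programming. The small downside is that a late finding first seen at the follow-up visit appears only in the total column.

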2.4 Study Endpoints

2.4.1 Primary Endpoints

Part A

Safety and tolerability

- Incidence, severity, and causality of AEs
- Incidence and severity of clinical laboratory abnormalities
- Change from baseline in vital signs (blood pressure, temperature, respiratory rate, and heart rate)
- Change from baseline in 12-lead ECG parameters
- Incidence and severity of AEs

Part B

- The change in pain from baseline during and after each infusion on a VAS 0-10 numerical rating scale of “pain now” with measures taken as the infusion starts and at 15 minute intervals for the first hour, then every thirty minutes for an additional two hours, then hourly until 6 hours from infusion commencement

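### The laboratory shift table selects a value by size of change before classifying it, so some out-of-range results can be shown as Normal (minor)

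*SAP*

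**What the plan says.** SAP 12.3.2 describes the table as "presenting a summary of the shifts from baseline values to the most extreme post-baseline value", and the pool of candidates is wide: "where all scheduled and unscheduled visit results will be assessed to determine the maximum shift". It then defines the value to use: "The maximum shift will be determined based on the absolute change from baseline, considering both shifts in the negative and positive direction". Classification comes last: "Both the baseline and maximum shift values will then be converted to “Low”, “Normal” or “High” using the associated reference ranges".

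The same section plans three other laboratory outputs:

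- **Listings**, in which "all laboratory parameters will be listed with flags for values outside the reference ranges".
- **Descriptive summaries** of values and changes by visit and treatment.
- **A worst-case table** of the categories Normal, Abnormal-NCS and Abnormal-CS, for which "The worst case finding will reflect all post-baseline assessments, including unscheduled and early discontinuation visits".

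The ECG shift table in SAP 12.7.2 ranks results by category, from best to worst, and not by size of change.

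SAP 2.4.1 names "Incidence and severity of clinical laboratory abnormalities" among the Part A primary endpoints.

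**The concern.** The reference range plays no part in choosing the value. The largest movement from baseline and the most abnormal result need not be the same measurement. When baseline lies near one limit, a small step across that limit loses to a larger step back into the middle of the range. The table then reports the harmless movement and drops the abnormal one.

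For a participant whose baseline is normal, the error runs one way: the rule can hide an abnormality but cannot create one. In a Part A dose column with six participants on active drug, each hidden case changes the displayed incidence by 1/6, about 17 percentage points.

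**Working it through.** The plan gives no figure on this point, so there is nothing to reproduce. The rule was applied as written.

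**Rule.** For baseline *b* and post-baseline values *v*, select the *v* with the largest |*v* − *b*|, then class it against the limits LLN and ULN.

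**Worked cases**, with an assumed range of 3.5 to 5.2:

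| Baseline | Post-baseline values (change) | Selected | Table shows | Lost |
|---|---|---|---|---|
| 5.0 Normal | 5.4 High (+0.4); 4.3 Normal (−0.7) | 4.3 | Normal to Normal | High |
| 3.6 Normal | 3.4 Low (−0.2); 4.2 Normal (+0.6) | 4.2 | Normal to Normal | Low |
| 5.0 Normal | 5.4 High (+0.4); 3.3 Low (−1.7) | 3.3 | Normal to Low | High |
| 4.35 Normal | 5.4 High (+1.05); 4.3 Normal (−0.05) | 5.4 | Normal to High | nothing |
| 5.0 Normal | 5.4 High only | 5.4 | Normal to High | nothing |

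Masking therefore needs at least two post-baseline values and a baseline nearer one limit than the other.

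**Limit on what can be hidden.** With a normal baseline, a High value *h* is displaced only by an in-range value *v* below baseline with *b* − *v* ≥ *h* − *b*. Hence *h* ≤ 2*b* − *v* ≤ 2×ULN − LLN. In the assumed range this is 2×5.2 − 3.5 = 6.9. For a parameter with a non-negative lower limit, a value above 2×ULN can never be shown as Normal.

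**Number of samples.** The Part A schedule (Protocol Section 3) marks laboratory tests at 6 hours on Days 1, 4 and 7 and on Days 3 and 6.

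- By dose received: Day 1 dose, two (6 h, Day 3); Day 4 dose, two (6 h, Day 6); Day 7 dose, one (6 h).
- Per participant over all days: 2 + 2 + 1 = 5.

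Protocol 21.1 and SAP 3.2.5 set Part A tabulations by dose, with pooled and total columns. SAP 12.3.2 asks for laboratory summaries by treatment but does not state the shift table's columns. Unscheduled results add to all these counts.

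**Simulation.** Assumptions: Gaussian values with total SD 1, range ±1.96, no drug effect, and a within-person variance share of 30% or 50%. The first result column is the share shown as Normal among participants with a normal baseline and at least one out-of-range post-baseline value.

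| Post-baseline samples | Shown as Normal, among those with an out-of-range value | Affected, among all with a normal baseline, per parameter |
|---|---|---|
| 1 | 0% | 0% |
| 2 | about 13% | about 0.8-1.1% |
| 5 | about 25-26% | about 3-4% |

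Letting the within-person correlation run from 0.3 to 0.9 gives 11-14% in the first result column with two samples and 23-26% with five. The median masked excursion is 0.14 to 0.22 SD beyond the limit. For excursions more than 1 SD beyond it, masking falls to about 1-2% with two samples and 2-6% with five. These are properties of the assumed model, not trial figures.

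**The case against.** The strongest reply is that little depends on this table. The primary endpoint concerns incidence and severity of abnormalities, and the output that matches it most closely is the worst-case table, which the shift rule does not touch. Every out-of-range value is flagged in the listings, and with 8 participants in Part A and up to 20 in Part B the listings can be read in full. The by-visit summaries include minimum and maximum, so scheduled-visit extremes are visible. No stopping rule uses the table, and clinically significant findings must be recorded as adverse events. A table of largest movements is also a legitimate display in itself.

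Most of this stands, and it is why the point is minor. Three stronger inferences are tempting, and the documents do not support them:

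- **That about a quarter of abnormal participants would be hidden because Part A schedules five samples.** Five applies only to a column that combines all days. By dose, the schedule gives two, two and one.
- **That the Part A primary endpoint is compromised.** The worst-case table and the flagged listings still capture these results.
- **That a large rise could pass as Normal.** The bound above rules this out for a normal baseline.

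What the reply does not remove is that the worst-case table carries neither direction nor a shift from baseline, and minima and maxima give no participant counts. The section also calls its selected value the most extreme one while defining it by change, and the two can differ.

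**Conclusion.** The defect is real and follows from the order of the two steps in SAP 12.3.2; the worked cases prove it without any distributional assumption. How often it would occur does rest on assumptions: the Gaussian model without drug effect, and the table's columns, which the SAP does not state. If the table is by dose, about 13% of normal-baseline participants with an out-of-range value would be shown as Normal for each of the first two Part A doses, and none for the third unless unscheduled samples are added. The 25-26% figure belongs to a per-participant or total column. Per parameter this is about 1% to 4% of all normal-baseline participants, and the hidden excursions are mostly small.

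The result is a misleading summary, not lost data. It is worth correcting because this is the only planned tabulation of Low/Normal/High movement from baseline. Severity is minor.

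**What to change.** In SAP 12.3.2, reverse the order: classify every post-baseline value, scheduled and unscheduled, against its reference range, then tabulate two shifts per parameter, baseline to highest category and baseline to lowest category. No participant with an out-of-range post-baseline value is then shown as Normal in both panels, and one with both Low and High results appears in both directions. In the first worked case the row changes from Normal to Normal into Normal to High in the highest-category panel. State the table's columns (by dose received, pooled, total) in the same place.

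The cost is a sentence or two in the SAP, a small programming change and two panels in place of one. No new data are needed.

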12.4 Vital Signs

12.4.1 Parameters

- Systolic Blood Pressure (SBP) (mmHg)
- Diastolic Blood Pressure (DBP) (mmHg)
- Heart Rate (beats/minute)
- Respiratory Rate (breaths/minute)
- Temperature (°C)

12.4.2 Biostatistical methods

Individually for Part A and Part B:

All vital signs data will be listed for all participants, with flags for values outside the site's reference range.

Vital sign parameters will be summarized by presenting summary statistics for observed values and change from baseline values for each scheduled visit and timepoint.

The incidence rates of notable vital sign abnormalities will be summarized using the following set of normal ranges:

- Systolic Blood Pressure (mmHg)
- Diastolic Blood Pressure (mmHg)
- Heart Rate (beats/min)
- Pulse Oximetry (%)
- Respiratory Rate breaths/min)
- Temperature (°C)

12.5 Body Measurements

12.5.1 Parameters

- Weight (kg)
- Height (cm)
- Body mass index (BMI) (kg/m²)

12.5.2 Biostatistical methods

BMI, height and weight data, will be listed for all participants.

Body measurement data will also be summarised.

